4.6 Rationale for Public health Emergency mitigation procedures

In the event of a Public Health emergency as declared by Local or Regional authorities i.e. pandemic, epidemic or natural disaster, mitigation procedures may be required to ensure participant safety and trial integrity and are listed in relevant sections of the study protocol. Notification of the Public Health emergency should be discussed with Novartis prior to implementation of mitigation procedures and permitted/approved by Local or Regional Health Authorities and Ethics Committees as appropriate.

Potential risk associated with the COVID-19 Pandemic

Novartis is committed to supporting the safety and wellbeing of our study participants, investigators and site staff. All local regulations and site requirements will be applied in the countries that are affected by the COVID-19 pandemic.

The Novartis clinical trial team will review the situation in each participating country and work with investigators to continue to ensure the safety of participants during the conduct of the trial. As the COVID-19 situation evolves, investigators must use their best judgement to minimize risk to participate during the conduct of the study. Lastly, the COVID mRNA vaccines consist of processed, mature mRNA, which are not expected to be a substrate for branaplam.

5 Study Population

As per the USM follow-up notification dated 06-Dec-2022, no further participants will be enrolled in this study. The inclusion and exclusion criteria in [Section 5.1](#) and [Section 5.2](#) below, were applicable to those participants enrolled to Cohort 1.

Approximately 75 male or female patients with confirmed Stage 1 or 2 HD and a UHDRS TFC score of >8 will be enrolled in this study to allow for approximately 25 participants per treatment arm. Fewer participants will be enrolled if all treatment arms are not opened. Manifest patients with a TFC >8 are selected because they are late enough in the disease process so that

mHTT can be measured in their CSF and clinical symptoms can be readily assessed, and early enough in the disease process so that they can comply with the protocol defined schedule of assessments during Core blinded treatment period (DRF and BE) and be monitored for disease progression and safety throughout the OLE. Eligible patients starting at the age of 25 will be enrolled to avoid the very high CAG repeats associated with early disease onset as these patients could be considered to have a more rapidly progressing phenotype. An age cap of 75 years is employed to avoid age-related comorbidities that typically occur above this age.

5.1 Inclusion criteria

Participants eligible for inclusion in this study must meet **all** of the following criteria:

1. Signed informed consent must be obtained prior to participation in the study.
2. Must be capable of providing informed consent (in the opinion of the Investigator)
3. Clinically diagnosed Stage 1 or 2 Huntington's disease with a diagnostic confidence level (DCL) = 4 and a UHDRS Total Functional Capacity (TFC) >8 at screening
4. Genetically confirmed Huntington's disease, with presence of ≥ 40 CAG repeats in the huntingtin gene.
 - For participants without prior documentation, a sample must be sent to the central study laboratory and confirmation of the CAG repeat length for these participants must be obtained prior to randomization
 - For participants with previously existing documentation of their CAG repeat length, it is acceptable to use this prior data to qualify for randomization. These participants must also submit a sample for CAG repeat testing to be conducted by the central study laboratory.
5. Male and female participants between 25 to 75 years of age, inclusive, on the day of Informed Consent signature

5.2 Exclusion criteria

Participants meeting any of the following criteria are not eligible for inclusion in this study:

1. Use of other investigational drugs within 5 half-lives of the first dose of study drug, or within 30 days, whichever is longer.
2. Prior participation in clinical trial investigating a huntingtin-lowering therapy (unless participant received only placebo)
3. History of hypersensitivity to any of the study drugs or its excipients or to drugs of similar chemical classes.
- 4a. Participants taking medications prohibited by the protocol ([Table 6-2](#) Prohibited Medications). In addition, participants should be on a stable dose and regimen of permitted chronic concomitant medications for at least 6 weeks prior to receiving the first dose of study drug which in the medical judgement of the Investigator is not anticipated to change during the study. If new medications are initiated during Screening, laboratory evaluations must meet eligibility criteria before first dose of study drug.
5. Any medical history, lumbar surgery or condition that would interfere with the ability to complete the protocol specified assessments, (e.g., history of brain or spinal injury that

would interfere with the LP or CSF circulation, implanted cerebrospinal shunt, conditions precluding MRI scans, herniated disc, etc.).

6. History of malignancy of any organ system (other than localized basal cell carcinoma of the skin or *in situ* cervical cancer), treated or untreated, regardless of whether there is evidence of local recurrence or metastases.
7. Participant has other severe, acute or chronic medical conditions including unstable psychiatric conditions, or laboratory abnormalities that in the opinion of the Investigator may increase the risk associated with study participation, or that may interfere with the interpretation of the study results.
8. Score “yes” on item 4 or item 5 of the Suicidal Ideation section of the C-SSRS, if this ideation occurred in the past 6 months from the Screening visit, or “yes” on any item of the Suicidal Behavior section, except for the “Non-Suicidal Self-Injurious Behavior” (item also included in the Suicidal Behavior section), if this behavior occurred in the past 2 years.
9. Pregnant or nursing (lactating) women. WOCB potential should not become pregnant during the study or within 7 months from stopping study medication.
- 10a. Sexually active males unwilling to use a condom during intercourse while taking study treatment and for 120 days (4 months) after the last dose of the study treatment. A condom is required for all sexually active male participants even if they are surgically sterile with a vasectomy to prevent them from fathering a child AND to prevent delivery of study treatment via seminal fluid to their female partner. In addition, male participants must not donate sperm for the time period specified above.

A condom is required to be used also by vasectomized men as well during intercourse with a male partner of the study participant.

The branaplam exposure in body fluids is not known. Since branaplam is genotoxic, sexual partners are advised to avoid direct contact with semen of participants, to prevent exposure to the study drug.

- 11a. **Women of child-bearing potential**, defined as all heterosexually active women physiologically capable of becoming pregnant, unless they are using one highly effective methods of contraception during dosing and for 7 months after stopping the study medication. Highly effective methods of birth control are those methods that have a less than 1% chance of an unwanted pregnancy for 1 year.

In addition to one highly effective method of contraception, a condom is required for all male partners of female participants to prevent fathering a child AND to prevent exposure of study treatment via vaginal fluid to your partner, until at least 7 months following the last dose of study treatment.

WOCB potential must not donate their eggs for 7 months after the last dose of study treatment.

Oral contraception cannot be considered due to potential decreased efficacy as potential DDI with branaplam.

Highly effective contraception methods include:

- Total abstinence (when this is consistent with the preferred and usual lifestyle of the participant). [Periodic abstinence (e.g., calendar, ovulation, symptothermal, post-ovulation

methods) and withdrawal are **NOT** acceptable methods of contraception for heterosexually active participants.]

- Female sterilization (have had surgical bilateral oophorectomy with or without hysterectomy) total hysterectomy or bilateral tubal ligation at least six weeks before taking investigational drug. In case of oophorectomy alone, only when the reproductive status of the woman has been confirmed by follow up hormone level assessment.
- Male sterilization of partners (at least 6 months prior to screening). For female subjects on the study, the vasectomized male partner should be the sole partner.
- Use of an intrauterine device (IUD) or intrauterine system (IUS) which is MRI compatible.

In case local regulations are more stringent than the contraception methods listed above to prevent pregnancy, local regulations apply and will be described in the ICF.

Women are considered post-menopausal if they have had 12 months of natural (spontaneous) amenorrhea with an appropriate clinical profile (e.g., age appropriate, history of vasomotor symptoms). Women are considered not of childbearing potential if they are post-menopausal or have had surgical bilateral oophorectomy (with or without hysterectomy), total hysterectomy or bilateral tubal ligation at least six weeks prior to Screening. In the case of oophorectomy alone, only when the reproductive status of the woman has been confirmed by follow up hormone level assessment is she considered not of childbearing potential.

The branaplam exposure body fluids is not known. Since branaplam is genotoxic, sexual partners are advised to avoid direct contact with vaginal fluid of participants, to prevent exposure to the study drug.

12a. History of:

- Gene therapy or cell transplantation or any other experimental brain surgery
- Hepatitis B or hepatitis C or serologic evidence for active viral hepatitis (HBsAg and HCVab test)
- Immunodeficiency diseases, including a positive human immunodeficiency virus (HIV) test result
- Current evidence of drug or alcohol abuse in the 12 months prior to screening, as defined by the DSM-V criteria for substance abuse. For former abusers, abstinence should be confirmed by laboratory tests (drug testing and/or CDT level in blood).
- Use of Tetra-Hydro-Cannabinoid (THC)/ cannabinoid containing substances is allowed as per local regulations and/or local medical practice if in the opinion of the Investigator, use does not represent an exclusionary condition, does not constitute abuse and does not affect cognition, and provided that participants are currently treated with a stable regimen for at least 12 weeks prior to first dose of study drug. Note: If initiated during the study, use must be withheld for 72 hours prior to any cognitive and/or motor assessments.

13a. Any surgical or medical condition which might put the participant at risk in case of participation in the study. The Investigator should make this determination in consideration of the participant's medical history and/or clinical or laboratory evidence of any of the following at the Screening visit:

- Unstable chronic gastrointestinal (GI) condition such as history of Crohn's disease, Ulcerative colitis, poorly controlled irritable bowel syndrome (IBS) or similar chronic GI conditions
- Neurologic or neuromuscular conditions other than HD
- History of or physical examination consistent with peripheral neuropathy or nerve conduction findings compatible with electrodiagnostic evidence of neuropathy
- Participants who have a known diagnosis of diabetes mellitus or who do not have a known diagnosis of diabetes with a glycated hemoglobin (HbA1c) > 6.5%
- Lipase, total bilirubin or amylase must not exceed the 1.5x ULN
- Liver disease or liver injury as indicated by abnormal liver function tests
 - Any of the following single parameters in serum of ALT, AST, GGT, and alkaline phosphatase must not exceed 2.0 x upper limit of normal (ULN).
- History of renal injury / renal disease or presence of severe impaired renal function as indicated by an estimated glomerular filtration rate (eGFR) using the modification of diet in renal disease (MDRD) equation < 30 (mL/min/1.73 m²) (allowing for age-related GFR decline in the mild to moderate range) or the presence $>3+$ proteinuria/ hematuria on a single (one time) repeated urinalysis.
- Evidence of urinary obstruction potentially leading to an impaired renal function at screening
- Diagnosis of testicular atrophy
- Diagnosis of primary ovarian failure
- Clinically significant retinal abnormalities on ophthalmologic examination by a local Ophthalmologist
- Active infection requiring systemic antiviral or antimicrobial therapy that will not be completed at least 3 days prior to first study drug administration (Day 1)
- Any objects and/or implants in the body which may be contraindicated for MRI, such as pacemakers and some IUD
- Diagnosis of chronic thrombocytopenia or a bleeding disorder

14a. Cardiovascular exclusion criteria:

- History or current diagnosis of ECG abnormalities indicating significant risk or safety concern for study participants such as: History of myocardial infarction, angina pectoris, heart failure, or coronary artery bypass graft (CABG).
- Screening ECHO abnormalities per investigator's medical judgement including but not limited to left ventricular ejection fraction (LVEF) $<50\%$.
- Screening or baseline not within normal range Troponin or NTproBNP values.
- History or concomitant clinically significant cardiac arrhythmias (e.g., sustained ventricular tachycardia, atrial fibrillation, etc.), complete left bundle branch block, high-grade atrioventricular (AV) block (e.g., bifascicular block, Mobitz type II and third-degree AV block).
- History of familial long QT syndrome or known family history of Torsade de Pointes risks for TdP including uncorrected hypokalemia or hypomagnesemia, history of

clinically significant/symptomatic bradycardia and a family history of idiopathic sudden death.

- Resting QTcF ≥ 450 msec (male) or ≥ 460 msec (female) at pretreatment [screening or baseline] (as mean of triplicate ECGs), or inability to determine the QTcF interval.
- Use of agents known to prolong the QT interval or with a known or possible risk of Torsade de Pointes unless it can be permanently discontinued or replaced with a permitted medication (refer to [Table 6-2](#)).

15a. Uncontrolled hypertension (average 3 systolic blood pressure [SBP]readings) at screening >140 mmHg or average diastolic blood pressure [DBP] > 90 mmHg excluding values related to white coat syndrome (anxiety-related), per Investigator's judgement. Any clinically significant hematological abnormality as assessed by the Site Investigator at screening and/or laboratory evidence of any of the following:

- INR, PT, or activated partial thromboplastin time (APTT) that are not within normal ranges
- Hemoglobin <110 g/L (females) or <120 g/L (males)
- Platelets $\leq 100 \times 10^9$ /L
- Platelets count $>500 \times 10^9$ /L
- Neutrophil count $<1.5 \times 10^9$ /L
- Leukocytes $<3.0 \times 10^9$ /L

6 Treatment

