
Co-medications eliminated via renal MATE2K transporter of clinical-relevant examples include, but are not limited to fexofenadine, glycopyrronium, metformin
 
Co-medications substrate of OCT1 transporter of clinical-relevant examples include, but not limited to cephalexin, dofetilide, pilsicainide, pindolol, procainamide, ranitidine, varenicline, umeclidinium, zidovudine.
 
For a complete list and additional information, please visit the FDA website noted above, on the respective tables and discuss with Sponsor
 
(in vitro: Table 4-1, clinics: Table 5-1).
	
Within 14 days prior to first study dose administration or during the study
	
If available, substitute with an alternative medication without MATE2K or OCT 1 transporter interaction, If no alternative is available then it should be taken with caution based on the Investigator's medical judgment

Medication(s) with a "Known Risk of Torsade de Pointes" per qtdrugs list (Woosley RL) These drugs include but are not limited to the following: escitalopram, citalopram, haloperidol, sulpiride, chlorpromazine, ondansetron, hydroxychloroquine ciprofloxacin, clarithromycin
 
For a complete list and additional information, please visit www.CredibleMeds.org (website) and discuss with Sponsor
	
Within 14 days prior to first study dose administration or during the study
	
Discontinue the prohibited medication and substitute with an alternative medication without known or potential risk. See below for use of drugs with conditional risk of TdP
 
After a patient has received study drug and if required due to life-threatening conditions or other exceptional circumstances indicating a high medical need for the use of these drugs the Investigator should use medical judgment carefully assessing benefit risk for an individual patient under consideration. However, ECG monitoring will be required before starting these drugs and repeated once again when steady state (5 half-lives) of this drug is achieved. In case of any abnormality on a single ECG (>480 QTc) triplicate ECGs should be performed and mean values should be used for confirmation (mean QTc > 480 ms).

Medications	Prohibition period	Action taken

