6.5.2.1 Dose adjustments for QTcF prolongation

As dose adjustments are not allowed, this section describes criteria for participant treatment interruption and permanent treatment discontinuation in case of QTcF prolongation. The Investigator should discontinue study treatment for a given participant if, on balance, he/she is of the opinion that continuation is not in the best interest of the participant or would be detrimental to the participant's well-being.

Clinically significant results or safety assessments that might put the participant at risk, including, but not limited to:

- Absolute QTcF >500 msec, confirmed by repeat ECG measurements
- Resting heart rate <30 or >120 bpm
- QRS >120 msec and increase >25% from Baseline
- Sustained ventricular tachycardia lasting 30 sec or more, ventricular fibrillation, or any hemodynamically compromising cardiac arrhythmia
- New complete heart block (Grade III AV block) or second-degree AV block Mobitz type II

In case of QTcF >500 msec (or QTcF prolongation >60 msec from baseline)

- Assess the quality of the ECG recording and the QT value and repeat if needed
- Interrupt study treatment
- Determine the serum electrolyte levels (in particular hypokalemia and hypomagnesemia). If abnormal, correct abnormalities before resuming study treatment.
- Review concomitant medication use for other causes for QT prolongation and for drugs with the potential to increase the risk of drug exposure related QT prolongation
- Check the dosing schedule and treatment compliance
- Consider collecting a time-matched PK sample and record time and date of last study treatment intake.

After confirming ECG reading at site, if QTcF >500 msec

- Interrupt study treatment
- Repeat ECG and confirm ECG diagnosis by a cardiologist or central ECG lab
- If QTcF confirmed >500 msec:

- Correct electrolytes, eliminate culprit concomitant treatments, and identify clinical conditions that could potentially prolong the QT as per the ECG and QTc Clinical Safety Standards Guidelines
- Consult with a cardiologist (or qualified specialist)
- Increase cardiac monitoring twice weekly until normalization or stabilization of the ECG findings, until the QTcF returns to ≤ 480 msec
- After resolution to ≤ 480 msec, consider permanent discontinuation of study drug treatment

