### **Summary tables**

- Absolute values and change from baseline will be summarized for continuous laboratory parameters by visit.
- For selected laboratory tests, the number and percentage of participants with newly occurring or worsening laboratory/liver enzyme abnormalities meeting the clinically notable criteria at any time post baseline will be summarized. Clinically notable criteria are defined in [Appendix 5.5](#).

For a participant to meet the criterion of a newly occurring clinically notable value, the participant needs to have a baseline value that is not clinically notable for that parameter. For a participant to meet the criterion of a worsening clinically notable value, the participant needs to have a baseline value that is clinically notable and also have a worse post-baseline value. For participants with missing baseline value, any post-baseline notable value will be considered as newly occurring.

For each participant, all applicable post-baseline values (including unscheduled or unplanned visits) will be checked against the respective criteria. If at least one of the results, for a particular parameter, exceeds the criteria, the participant will be considered as clinically notable abnormal for that parameter. A participant can be counted in both low and high categories. If multiple

abnormality occurrences exist for the same lab parameter, the worst case within a lab parameter will be used to categorize the abnormality.

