##### Summary tables

- Absolute values and change from baseline will be summarized for ECG parameters by visit and time point.
- The number and percentage of participants with newly occurring or worsening ECG abnormalities at any post-baseline visits will be summarized.

For derivation of notable values of triplicate ECG, the mean of the triplicate ECGs will be used. Notable criteria are defined in [Appendix 5.5](#).

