**Table 5-10 Abnormal ranges for ECG**

ECG Parameter	Abnormality Flags	
	Lower bound	Upper bound
Notable value		
HR	<50 bpm or $\leq -15$ bpm change from baseline	>120 bpm or $\geq 15$ bpm change from baseline
RR Interval	< 600 msec	> 1200 msec
PR interval	< 120 msec	> 200 msec
QRS Interval	< 60 msec	> 109 msec
QT Interval	< 320 msec	> 450 msec
QTcF Interval (Fridericia's correction)	< 320 msec	> 450 msec
Notable relative change from previous visit		
QTcF Interval (Fridericia's correction)	$\leq -20\%$ ;	$\geq 20\%$

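### The SAP's QTcF count has one upper limit (>450 ms) and a 20% row, so it neither separates values above 500 ms nor captures the protocol's >60 ms rise from baseline

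*Protocol*

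**What the plan says.** **SAP 5.5, Table 5-10.** The absolute rule is one row for everyone: "QTcF Interval (Fridericia's correction) < 320 msec > 450 msec". The only other QTcF rule stands under "Notable relative change from previous visit" and flags a change of 20% or more in either direction.

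**SAP 2.7.4.1 (ECG).** The table is applied as follows: "The number and percentage of participants with newly occurring or worsening ECG abnormalities at any post-baseline visits will be summarized". ECG data are listed for participants with at least one abnormal value. Values and changes from baseline are summarised by visit and time point. The ECG section does not define worsening. The only definition is in SAP 2.7.3 for laboratory data: "the participant needs to have a baseline value that is clinically notable and also have a worse post-baseline value".

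**Protocol 5.2, item 14a.** Men are excluded from 450 ms upward, women from 460 "msec (female) at pretreatment [screening or baseline] (as mean of triplicate ECGs), or inability to determine the QTcF interval".

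**Protocol 6.5.2.1.** The list of results that may put a participant at risk includes an absolute QTcF above 500 "msec, confirmed by repeat ECG measurements". Study treatment is interrupted above 500 ms or on a rise of more than 60 ms from baseline. A value of 480 ms or below is the resolution level after a confirmed value above 500 ms.

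**Protocol 6.2.2, Table 6-2.** If a single ECG exceeds 480 ms after a co-medication with torsade risk is started, "triplicate ECGs should be performed and mean values should be used for confirmation".

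**The concern.** The ECG count table shows, by arm, how many participants had a QTcF problem. Its single upper limit lies below the women's entry limit and well below the protocol's interruption level. One n (%) can therefore mix small fluctuations around 450 ms with events that required drug interruption. A rise large enough to meet the protocol's change-from-baseline trigger can miss the count altogether.

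Protocol 4.5 reports hERG inhibition and a positive concentration-QTcF slope, and it lists cardiovascular effects as a potential risk. Cohort 1 was planned at about 25 participants, randomised 4:1, so about 20 active and 5 placebo. In groups that small, a few chance crossings of 450 ms blur the comparison between arms.

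**Working it through.** The documents give no expected QTcF outlier count, so there is no stated figure to reproduce.

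**1. Thresholds side by side**

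| Level | Protocol use | Own row in SAP Table 5-10? |
|---|---|---|
| 450 ms | men's entry limit | yes (>450, both sexes) |
| 460 ms | women's entry limit | no |
| 480 ms | co-medication confirmation; resolution after >500 | no |
| 500 ms | interruption | no |
| +60 ms from baseline | interruption | no |

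An eligible woman at 451-459 ms is already notable. Under the laboratory definition of worsening, any higher later value counts her. An eligible man is below 450 ms at the eligibility ECG.

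**2. Can the 20% row stand in for the 60 ms trigger?**
- 20% equals 60 ms only at 60 / 0.20 = 300 ms, which is below the SAP's own lower bound of 320 ms.
- 20% of 320, 420 and 450 ms is 64, 84 and 90 ms.
- A rise to 500 ms meets the row only from 500 / 1.20 = 416.7 ms or lower.
- The row refers to the previous visit, not to baseline, so a gradual rise escapes it.
- Example: 380 to 445 ms is +65 ms, and 65 / 380 = 17.1%. It exceeds 60 ms but is below 20% and not above 450 ms. It is neither counted nor listed as a QTcF abnormality, although the participant could be listed for another ECG parameter.

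**3. Size of the drug effect**
The slope in Protocol 4.5 is 0.04912 ms per ng/mL. The predicted steady-state Cmax at 56 mg in Protocol 4.2 is 40.8 ng/mL. The predicted mean effect is 0.04912 x 40.8 = 2.0 ms.

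**4. Sensitivity near 450 ms (assumed inputs)**
The documents give no sex mix, QTcF mean or SD. Assumptions: within-person SD 5, 8 or 10 ms; between-person SD 15 ms; male mean 405 or 415 ms; women 0, 5 or 10 ms higher. Protocol Table 8-8 and the revised Week 33 visit give 14 post-baseline ECG time points to Week 33.

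For a man with usual level m, no drug effect and a baseline below 450 ms, P(any value >450) = 1 - [Phi((450 - m)/SD)]^14. At m = 445:
- SD 5: 1 - 0.8413^14 = 0.91
- SD 8: 1 - 0.7340^14 = 0.99
- SD 10: 1 - 0.6915^14 = 0.99

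Simulation gives women at the same usual level 0.87-0.97. They are slightly lower because a woman who starts at 451-459 ms must exceed her own baseline.

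Share of eligible participants affected, with the 2 ms shift, across the assumed ranges:

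| Event | Women | Men |
|---|---|---|
| newly occurring or worsening, >450 ms | 1-33% | 1-14% |
| already >450 ms at baseline | 0.2-6% | none, by eligibility |
| 460 ms or more | 0.2-14% | not computed |
| >480 ms | at most 0.6% | at most 0.05% |
| >500 ms | about 0 | not computed |

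At a 50:50 sex mix, women make up 52-55% of flags if the sexes have equal mean QTcF, 62-72% if women are 5 ms higher, and 70-83% if 10 ms higher.

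These runs treat every reading as a triplicate mean. SAP 2.7.4.1 says triplicates are taken only at Weeks 1 and 9, while Protocol 8.4.2 requires them at all scheduled time points. Single readings vary more, so the two statements should be reconciled.

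**The case against.** **Trigger-level cases remain visible elsewhere.** SAP 2.7.4.1 summarises values and changes from baseline by visit, and SAP 2.1 includes minimum and maximum. A value above 500 ms would be listed, would require interruption, and could appear among adverse events leading to interruption. This stands: in a cohort of about 25, a 505 ms value would not be lost. The gap is in the count table. For a rise above 60 ms that ends at or below 450 ms, it is also in the QTcF criterion for the listing.

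**Extra rows would not detect a 2 ms shift.** This also stands. The change-from-baseline summaries address that question; the rows only separate trigger-level events.

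**Entry and notable limits may differ.** Platelets at or below 100 x 10^9/L exclude, while the notable limit is 50. The healthy-volunteer outlier analysis in Protocol 4.5 also used >450 ms without a sex split. This argues for keeping the >450 row. The same analysis also reported >480 ms, >30 ms and >60 ms, which supports adding rows.

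**Stakes are modest.** Dosing ended in August 2022, development in Huntington's disease was discontinued for neurotoxicity, and reporting is descriptive in an abbreviated study report. This limits the priority, not the correctness of the point.

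A reader might also infer that the count is driven by normal variation in women. The documents do not show that: they give no sex mix or QTcF distribution, and men with the same usual level near 450 ms are flagged almost as easily. Nor do they make 480 ms a general action level for study drug. It is a confirmation level for certain co-medications and a resolution level after a confirmed value above 500 ms.

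**Conclusion.** The concern holds as a gap in the categorical ECG reporting. Three parts follow from the documents without assumptions: there is one >450 ms limit with no higher tier; women can enter at 451-459 ms with no ECG-specific rule for handling that baseline; and neither the >500 ms nor the >60 ms limb of the interruption rule has a row, with the 20% row unable to replace the second.

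That the count reacts to ordinary variation near 450 ms follows in direction from the any-visit rule. Its size rests on assumed means, SDs and 14 ECGs per participant. If half of the 20 planned active participants were women (also an assumption), 1-33% would be 0.1 to 3.3 women flagged.

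The documents do not support saying that the 450 ms limit is wrong or must be replaced by the entry limits. The point is a cheap improvement in reporting, not a threat to the study's safety conclusions.

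**What to change.** In SAP Table 5-10 and the ECG summary in SAP 2.7.4.1:
- Keep the >450 ms row, for comparability with the healthy-volunteer analysis.
- Add separate rows by arm, as newly occurring counts, for >480 ms, >500 ms and an increase of more than 60 ms from baseline.
- Optionally add a row using the sex-specific entry limits of item 14a (men 450 ms or more, women 460 ms or more).
- State that a baseline already above 450 ms is not counted as newly occurring, and show such participants on a separate line.

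Because the listing depends on having an abnormal value, adding the >60 ms row also brings those participants into it. The rows are reporting categories taken from levels the protocol already uses, and no clinical rule changes.

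Cost: a few table rows and a sentence of SAP text, with no new data. Downside: most of the added rows are likely to be near empty. SAP Table 5-15 already grades liver tests in tiers, so the format is familiar.
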